# 7.2. Visit 2 (Day 8 [Window: Days 8-15])

All subjects will return for Visit 2 on Day 8 (Window: Days 8-15) at which time the following assessments will be performed.

- Review changes in medical history:
  - Review symptoms of BV since Visit 1 and treatments for BV other than investigational drug.
  - Review all concomitant medications since Visit 1.
- Review for sexual intercourse, insertion of intravaginal substances, or objects since Visit 1.
- Review for AEs and SAEs.
- Review Memory Aid and collect applicator kit.
- Perform targeted general physical exam based on symptoms.
- Perform gynecologic exam of cervix, vagina, and vulva:
  - Assessment of vaginal discharge (quantity, color, odor, and consistency).
  - Record presence or absence of objective signs of inflammation of cervix, vagina and vulva (edema, erythema, excoriation) and presence or absence of lesions.
- Collect vaginal secretions for pH testing using pH paper 4-6.
- Perform KOH 10% wet mount on vaginal (must be performed by a licensed clinician or trained laboratory personnel) and record "whiff test": fishy (amine) odor released by the addition of a drop of 10% KOH to the vaginal discharge.
  - Evaluate for pseudohyphae or budding spores (must be performed by a licensed clinician or trained laboratory personnel).
- Perform saline wet mount (must be performed by a licensed clinician or trained laboratory personnel).
  - Evaluate and record presence and percent of 'Clue' cells in vaginal secretions.
  - Record for presence of flagellated protozoa (if positive, refer to provider for further therapy).
- Collect vaginal swabs for:
  - Gram stain of vaginal smear.
  - Swabs for culture of Gardnerella spp., Mobilluncus spp., Lactobacilli spp., Candida spp.
  - Future Use: If the subject consents to future use, one Copan ESwab in liquid amies will be collected for future use (to be transported on cold packs or ice to the research laboratory).

- Obtain approximately 10 cc of blood for:
  - WBC count, hemoglobin, platelet, neutrophil count.
  - Creatinine, ALT, AST, total bilirubin, random glucose.
- Counsel subjects to refrain from penile-vaginal or receptive oral sexual intercourse or insertion of any substance, products, or objects into vagina for 48 hours prior to Visit 3.
- Counsel subjects on avoidance of pregnancy (for all female subjects of childbearing potential).

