# 7.3. Visit 3, Final Study Visit (Day 28 [Window: Days 22-31])

All subjects will return for Visit 3 on Day 28 (Window: Days 22-31) at which time the following assessments will be performed:

- Review changes in medical history.
- Review all concomitant medications since Visit 2.
- Review of BV symptoms and treatments for BV other than investigational drug.
- Review history of sexual intercourse, insertion of intravaginal substances or objects within the past 48 hours.
- Review Memory aid if solicited events continued at last visit and collect applicator kit, if not done at Visit 2.
- Review AEs/SAEs: If AEs or SAEs continue at Visit 3, the study team will follow until resolution or stabilization of the event. Laboratory abnormalities that were stable at Visit 2 (i.e., were abnormal at Visit 1 prior to receipt of study drug and continued to be abnormal but no worse at Visit 2) do not need to be repeated and are considered stabilized. Laboratory abnormalities that occurred between Visit 1 and Visit 2 or worsened at Visit 2 should be repeated until the test has stabilized or resolved.
- Perform targeted general physical exam based on symptoms.
- Gynecologic exam of cervix, vagina, and vulva:
  - Assessment of vaginal discharge (quantity, color, odor, and consistency)
  - Assess cervix, vagina, and vulva for presence or absence of objective signs of inflammation (edema, erythema, excoriation) and/or genital lesions.
- Collect vaginal secretions for pH testing using pH paper 4-6.

- Perform KOH 10% wet mount on vaginal secretions (performed by licensed clinician or trained laboratory personnel)
  - Record "whiff test": fishy (amine) odor released by the addition of a drop of 10% KOH to the vaginal discharge.
  - Evaluate for pseudohyphae or budding spores (performed by a licensed clinician or trained laboratory personnel).
- Perform saline wet mount (performed by a licensed clinician or trained laboratory personnel).
  - Evaluate and record presence and percent of "clue cells" in vaginal secretions.
  - Record for presence of flagellated protozoa (if positive, refer to provider for further therapy).
- Collect vaginal swabs for:
  - Gram stain of vaginal smear
  - Swabs for culture of *Gardnerella spp.*, *Mobilluncus spp.*, *Lactobacilli spp.*, and *Candida spp.*

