#### 7.5. Unscheduled Visit

Unscheduled visits may occur at any time during the study. The procedures below are to be performed at any unscheduled visit. See the MOP for instructions for documentation and data reporting.

- Obtain interim medical history and solicit information on vaginal symptoms.
- Perform a targeted physical exam if indicated based on symptoms.
- Perform gynecological exam and collect appropriate samples (e.g., appropriate clinical samples for genital infectious pathogens).

- Review concomitant medications.
- Review of memory aid, if applicable.
- Review of AEs/SAEs, if applicable.

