-  Safety Laboratories Include: White blood cell count, hemoglobin, platelet count, absolute neutrophil count, creatinine, ALT, AST, total bilirubin, random glucose, HIV test (Visit 1 only).
- { } Targeted physical examination if indicated based on review of symptoms.
- [] Subjects will be called regarding grade 3 laboratory abnormalities within 24 hours of receipt of results and told to discontinue study product. Subjects with positive HIV, chlamydia or gonorrhea tests will be contacted as soon as possible after results are available and referred to their primary care provider for appropriate treatment.
- \*Memory Aid will be reviewed only if solicited events continued at Visit 2. Study Drug Kit returned only if not returned at Visit 2.
- \* If subject declines to return for an in-person visit, the study personnel will ask to contact the subject by telephone to assess for AE/SAEs on Day 22-31.
- † Evaluate cervix, vagina, and vulva. Collect appropriate clinical samples for genital infectious pathogens.
- \*\* Assess for vaginal discharge (quantity, color, odor, and consistency) and record presence or absence of objective signs of inflammation of cervix, vagina, and vulva (edema, erythema, excoriation).
- ^ Laboratory abnormalities that occurred between Visit 1 and Visit 2 or worsened at Visit 2 should be repeated until resolved or has stabilized. Further testing beyond Visit 3 is at the discretion of the PI or study investigator.

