3.3.9. Treatment Compliance

Compliance is assessed by the study coordinator's count of used/unused applicators in each returned subject kit. If a kit is not returned, compliance will be assessed by the subject's self-report on the memory aid. If an incomplete kit is returned, the subject's self-report will be used in conjunction with the count of used/unused applicators to determine subject compliance. In addition to the count of used/unused applicators, the timing of dosing will be considered. Subjects are instructed to administer study product twice daily (morning and evening) with at least 8 hours between doses. If the subject received her first dose after 3 pm, she will be instructed to administer the next dose the following morning. A subject is compliant if she uses at least 5 of 6 doses and they were administered within 72 hours from the first dose, at least 8 hours apart, and if no more than 2 doses in a 24 hour period are taken.

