⁶ Safety Laboratories Include: White blood cell count, hemoglobin, platelet count, absolute neutrophil count, creatinine, ALT, AST, total bilirubin, random glucose, HIV test (*Visit 1 only*).

{} Targeted physical examination if indicated based on review of symptoms.

[] Subjects will be called regarding grade 3 laboratory abnormalities within 24 hours of receipt of results and told to discontinue study product. Subjects with positive HIV, chlamydia or gonorrhea tests will be contacted as soon as possible after results are available and referred to their primary care provider for appropriate treatment.

⁺ Memory Aid will be reviewed *only* if solicited events continued at Visit 2. Study Drug Kit returned *only* if not returned at Visit 2. * If subject declines to return for an in-person visit, the study personnel will ask to contact the subject by telephone to assess for AE/SAEs on Day 22-31.

[†] Evaluate cervix, vagina, and vulva. Collect appropriate clinical samples for genital infectious pathogens.

[#] Assess for vaginal discharge (quantity, color, odor, and consistency) and record presence or absence of objective signs of inflammation of cervix, vagina, and vulva (edema, erythema, excoriation).

^ Laboratory abnormalities that occurred between Visit 1 and Visit 2 or worsened at Visit 2 should be repeated until resolved or has stabilized. Further testing beyond Visit 3 is at the discretion of the PI or study investigator.

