9.2. Measurements of Treatment Compliance

All subjects are to receive a total of six doses of study product (twice daily for three consecutive days). The first dose is administered in clinic and the remaining 5 doses will be administered by the subject at home. Subjects record the timing of all remaining doses on a memory aid, which is reviewed with clinic staff at Visit 2. Compliance is assessed by the study coordinator's count of used/unused applicators in each returned subject kit. If a kit is not returned, compliance will be

assessed by the subject's self-report on the memory aid. If an incomplete kit is returned, the subject's self-report will be used in conjunction with the count of used/unused applicators to determine subject compliance. In addition to the count of used/unused applicators, the timing of dosing will be considered. Subjects are instructed to administer study product twice daily (morning and evening) with at least 8 hours between doses. If the subject received her first dose after 3 pm, she will be instructed to administer the next dose the following morning. A subject is compliant if she uses at least 5 of 6 doses and they were administered within 72 hours from the first dose, at least 8 hours apart, and if no more than 2 doses in a 24 hour period are taken.

If a subject is found to have a positive test for HIV, chlamydia or gonorrhea or a Grade 3 laboratory abnormality from Visit 1, she will be notified of the results, withdrawn from receiving further study product, but will be followed for safety and efficacy. All subjects who were randomized will be followed for safety and efficacy. If any subject experiences a severe AE related to the study product, further doses will be discontinued.

The dates of first treatment are presented for subjects in the Safety population by site in **Table 19** and actual treatment group in **Table 20**. The number of subjects not compliant with study treatment will be presented by treatment group as part of the subject disposition table (**Table 5**). The number of doses administered as scheduled and out of window is summarized for subjects in the Safety population by site in **Table 21** and by actual treatment in **Table 23**.

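### The Visit 3 schedule gives the drug kit a catch-up clause but the memory aid none, so a diary not seen at Visit 2 is not scheduled for review

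*Protocol*

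**What the plan says.** **Collection.** Under protocol 9.2.2 and SAP 4.5 the subject records solicited vulvovaginal events on a memory aid for five days from Day 1, and goes on recording any symptom still present until it resolves. The planned review is at Visit 2, where protocol 7.2 says: "Review Memory Aid and collect applicator kit".

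**Visit 3.** The protocol Table 5 footnote says: "Memory Aid will be reviewed only if solicited events continued at Visit 2. Study Drug Kit returned only if not returned at Visit 2". SAP Table 1 has the same rule, with the restriction emphasised: "Memory Aid will be reviewed *only* if solicited events continued at Visit 2". Protocol 7.3 words it differently: "Review Memory aid if solicited events continued at last visit and collect applicator kit, if not done at Visit 2".

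**Use of the diary.** Treatment-emergent solicited urogenital events through Visit 2 are the first primary safety endpoint, compared between arms by Fisher's exact test (SAP 9.3.1). For dosing, SAP 9.2 says: "Subjects record the timing of all remaining doses on a memory aid, which is reviewed with clinic staff at Visit 2". SAP 3.3.9 adds: "If a kit is not returned, compliance will be assessed by the subject's self-report on the memory aid". The same section sets timing limits for compliance: within 72 hours of the first dose, at least 8 hours apart, and no more than two doses in 24 hours.

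**Denominators.** SAP 9.3 bases adverse event incidence on the whole safety population, and the Table 62 shell follows that rule. The severity summaries in SAP 9.3.1 (Table 64) use only subjects with non-missing data.

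**The concern.** The footnote handles two items that should both come back at Visit 2. For the kit it asks whether the item has been returned. For the diary it asks whether symptoms were continuing, which is a different question. That suits its evident purpose of following unresolved symptoms, but it leaves out the diary that has not been seen at all.

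A site that follows the schedule as written could leave a completed diary unreviewed. Two things depend on that diary: the Day 1-5 solicited-event record for a tested primary safety outcome, and the times of doses 2 to 6, for which the SAP names no other source. Under the incidence denominator the error runs one way, towards under-reporting of local reactions.

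**Working it through.** The plan attaches no figure to this point. The check is mainly a comparison of texts, followed by arithmetic for scale.

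**1. Apply the footnote to each kind of woman attending Visit 3.**

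| At Visit 2 | Kit due at Visit 3? | Diary due at Visit 3? |
|---|---|---|
| Attended with diary and kit, symptoms resolved | No, already returned | No, already reviewed |
| Attended with diary, symptoms continuing | Only if not returned | Yes |
| Attended without diary, no symptoms known to continue | Only if not returned | **No** |
| Did not attend | Yes | **No**: there was no Visit 2 finding that events continued |

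The last two rows are the gap. In both, the diary has not been reviewed and the rule does not call for it.

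**2. Read protocol 7.3 both ways.** Its closing clause, after the comma, can attach to the kit alone, which is the more natural reading and matches the footnote. It can also attach to both actions. In that case the protocol body permits catch-up, while the protocol and SAP schedules restrict review with the word *only*. Either the gap is real or the texts disagree, and both need the same edit.

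**3. What each affected woman loses.**
- *Solicited events.* Without the diary her Day 1-5 grades are missing. She stays in the SAP 9.3 denominator, so she contributes no event unless one was captured another way. In the Table 64 severity summary she drops out of the denominator, so the two tables would report different rates.
- *Dose timing.* The time of dose 1 is on the CRF (protocol 6.4) and the dose count comes from the applicators, but the SAP 3.3.9 limits cannot be checked for doses 2 to 6. If the kit is also missing, the fallback for the count is the same diary.
- *Per-protocol set.* SAP 6.3.5 generally requires a Visit 2 attended within its window. A woman who missed Visit 2 is therefore usually outside the set already. The timing problem matters mainly for women who attended without the diary.

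**4. Scale per woman.** Assume all 120 planned subjects are treated, at 2:1: 120 × 2/3 = 80 active and 120 × 1/3 = 40 placebo. One woman whose true event goes uncounted lowers the reported incidence by 1/80 = 1.25 percentage points on active, or 1/40 = 2.5 points on placebo.

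**5. Scale if a share d goes unused equally in both arms.** Reported rate = true rate × (1 − d), and the difference between arms shrinks by the same factor. As a check on the power calculation, exact enumeration of the two-sided Fisher test at 60 versus 30 with rates 0.50 and 0.20 gives 0.783, against .78 in protocol Table 4. At 80 versus 40, with assumed true solicited-event rates of 0.50 and 0.20:

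| Assumed d | Reported rates | Power, counted as no event | Power, excluded instead |
|---|---|---|---|
| 0 | 0.50 vs 0.20 | 0.899 | 0.899 |
| 5% | 0.475 vs 0.19 | 0.878 | 0.893 |
| 10% | 0.45 vs 0.18 | 0.852 | 0.866 |
| 20% | 0.40 vs 0.16 | 0.780 | 0.812 |

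This shows what any unused diary costs, whatever the cause. It does not estimate the footnote's effect, since the documents give no value of d.

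**The case against.** The strongest reply is that the footnote governs one scheduled action at one visit, and other routes remain.

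- Protocol 7.5 lists, for unscheduled visits, "Review of memory aid, if applicable".
- Table 5 marks diary review at early termination.
- SAP 3.3.8 lets an unscheduled Visit 2 stand in for a missed one.
- Protocol 5.3.4 requires phone and certified-mail efforts to recall women who miss a visit.
- Staff take a history of the same genital symptoms (protocol 8.1). SAP Listing 11 shows clinical severity assessments at Visits 1, 2 and 3. New or worsening solicited symptoms of grade 2 or higher prompt contact with the site (protocol 5.3.3).
- Nothing forbids accepting a late diary. The outcome is defined by when the event occurred, not when the diary was read, so Day 1-5 entries handed in late already qualify.

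Much of this stands. A reader might infer from the footnote that a diary missed at Visit 2 is never recovered and its data are lost. The documents do not support that; they support only that review at Visit 3 is not scheduled.

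The other routes do not close the gap completely. Early termination is for women who withdraw, not those attending Visit 3. The unscheduled-visit review is conditional, and Table 5 has no mark for it in that column. Recall may bring a woman back, but if she returns at Visit 3 the footnote still applies. A history taken on Day 22-31 asks her to recall daily grades from 17 to 26 days after Day 5 (22 − 5 = 17; 31 − 5 = 26).

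**Conclusion.** The point holds in a limited form. The two schedules restrict Visit 3 diary review to continuing events, the kit has a catch-up that the diary lacks, and protocol 7.3 does not settle the matter. Followed literally, the rule leaves some retrievable Day 1-5 event data and home dose times unused, and the incidence denominator turns such gaps into apparent non-events.

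The size is unknown and probably small. Three broader readings should not be drawn:

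- *Primary safety as a whole.* The second primary safety outcome, product-related SAEs through Visit 3, does not depend on the diary.
- *A loss rate.* The share of women with no diary reviewed at Visit 2 would be too large a measure. It includes women who never return, whom the footnote does not affect, and women reached by other routes. The documents give no rate for either group.
- *A parallel gap in safety bloods.* The laboratory footnote, "Laboratory abnormalities that occurred between Visit 1 and Visit 2 or worsened at Visit 2 should be repeated until resolved or has stabilized", also ties Visit 3 testing to earlier findings. But the laboratory adverse event outcome ends at Visit 2 (protocol 3.2.1, SAP 3.2.5), so a later sample could not contribute to it. Nothing is asked for here.

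The change is still worth making: it concerns a tested primary safety outcome, the asymmetry is plain, and the remedy is one clause.

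**What to change.** Use one sentence in protocol 7.3, the protocol Table 5 footnote and the SAP Table 1 footnote: *Memory aid reviewed at Visit 3 if it was not reviewed at Visit 2, or if solicited events continued at Visit 2.*

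In SAP 9.3.1 and 3.3.9, state that diaries first reviewed at Visit 3 are used for the solicited-event outcome and for dose timing. In 9.3.1, also say how a woman with no diary at all is counted in Tables 62 and 63, so that these can be reconciled with Table 64. The SAP sentences can be added at any time before database lock.

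The cost is a footnote, a bullet and a few SAP sentences, plus a few minutes at Visit 3 for the women concerned. The downside is that those diaries are reviewed somewhat later than planned. No new procedure is needed.

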# **APPENDIX B: Toxicity Table**

**Table 6:** Toxicity Table

HEMATOLOGY	Mild (Grade 1)	Moderate (Grade 2)	Severe (Grade 3)
Hemoglobin (Female) - g/dL	11.0-11.5	9.5-10.9	<9.5
WBC Increase - cell/mm3	11,001- 15,000	15,001-20,000	>20,000
WBC Decrease - cell/mm3	2,500-3,500	1,500-2,499	<1500
Platelets Decreased - cell/mm3	120,000- 130,000	100,000- 119,999	<100,000
Neutrophils Decrease - cell/mm3	1,500-1,799	1,000-1,499	<1000
CHEMISTRIES			
Glucose – Hypoglycemia mg/dL	60-64	55-59	<55
Glucose – Hyperglycemia Random – mg/dL	140-159	160-200	>200
Creatinine – mg/dL	>ULN-1.7	1.8-2.0	>2.0
AST U/L	44-105	106-175	>175
ALT U/L	34-105	106-175	>175
Bilirubin (serum total) mg/dL	1.3-2.0	2.1-2.5	> 2.5

ATC	Anatomical Therapeutic Classification
BV	Bacterial Vaginosis
CDC	Centers for Disease Control and Prevention
CI	Confidence Interval
CIN	Cervical intraepithelial neoplasia
CRF	Case Report Form
CSR	Clinical Study Report
DMID	Division of Microbiology and Infectious Diseases
DSMB	Data and Safety Monitoring Board
EDC	Electronic Data Capture
ER	Emergency Room
F	Fahrenheit
FDA	Food and Drug Administration
GML	Glycerol monolaurate
HEENT	Head, Ears, Eyes, Nose, and Throat
HIV	Human Immunodeficiency Virus
HSIL	High grade Squamous Intraepithelial Lesion
ICH	International Conference on Harmonisation
IRB	Institutional Review Board
ITT	Intention to Treat
kg	kilogram
КОН	Potassium Hydroxide
L	Liter
LLN	Lower Limit of Normal
LOCF	Last observation carried forward
MedDRA	Medical Dictionary for Regulatory Activities

mg	Milligram
mITT	Modified Intention to Treat
mL	Milliliter
Ν	Number (typically refers to subjects)
NAAT	Nucleic Acid Amplification Test
NF	National Formulary
NIH	National Institutes of Health
рН	Potential of Hydrogen
PI	Principal Investigator
РР	Per Protocol
РТ	Preferred Term
SAE	Serious Adverse Event
SAP	Statistical Analysis Plan
SD	Standard Deviation
SDCC	Statistical and Data Coordinating Center
SGOT	Serum glutamic oxaloacetic transaminase
SGPT	Serum glutamate pyruvate transaminase
SMC	Safety Monitoring Committee
SOC	System Organ Class
SOP	Standard Operating Procedures
TOC	Test of Cure
U	Units
ug	microgram
ULN	Upper Limit of Normal
WBC	White Blood Cell
WHO	World Health Organization

LIST OF ABBREVIATIONS (continued)

1. **PREFACE**

The Statistical Analysis Plan (SAP) for "A Phase II, Double-Blind, Randomized, Placebo-Controlled, Multicenter Trial to Assess the Safety and Efficacy of 5% Monolaurin Vaginal Gel Administered Intravaginally for the Treatment of Bacterial Vaginosis" (Division of Microbiology and Infectious Diseases (DMID) Protocol 12-0021) describes and expands upon the statistical information presented in the protocol.

This document describes all planned analyses and provides reasons and justifications for these analyses. It also includes sample tables, listings, and figures planned for the final analyses. Regarding the final analyses and Clinical Study Report (CSR), this SAP follows the International Conference on Harmonisation of Technical Requirements for Registration of Pharmaceuticals for Human Use (ICH) Guidelines, as indicated in Topic E3 (Structure and Content of Clinical Study Reports), and more generally is consistent with Topic E8 (General Considerations for Clinical Trials) and Topic E9 (Statistical Principles for Clinical Trials). The structure and content of the SAP provides sufficient detail to meet the requirements identified by the Food and Drug Administration (FDA) and ICH, while all work planned and reported for this SAP will follow internationally accepted guidelines published by the American Statistical Association and the Royal Statistical Society for statistical practice.

This document contains four sections: (1) a review of the study design, (2) general statistical considerations, (3) comprehensive statistical analysis methods for efficacy and safety outcomes, and (4) a list of proposed tables and figures. Any deviation from this SAP will be described and justified in the CSR. The reader of this SAP is encouraged to also review the study protocol for details on conduct of the study and the operational aspects of clinical assessments.

